### **Adverse Events by Maximum Relationship**

Treatment-emergent AEs also will be summarized by maximum relationship of each preferred term to study drug (DAAs), as assessed by the investigator. If a subject has an AE with unknown relationship, then the subject will be counted in the relationship category of "unknown," even if the subject has another occurrence of the same event with a relationship present. The only exception is if the subject has another occurrence of the same AE with a relationship assessment of "Reasonable Possibility." In this case, the subject will be counted under the "Reasonable Possibility" category.

### **11.2.3 Adverse Events of Special Interest**

Adverse events of special interest include the following:

- Hepatic decompensation/hepatic failure events, identified using the AbbVie Product MedDRA Query (PMQ) for Hepatic Decompensation and Hepatic Failure.
- Hepatocellular carcinoma events, identified using the preferred terms of hepatocellular carcinoma, hepatic neoplasm, hepatic cancer, hepatic cancer metastatic, and hepatic cancer recurrent.

For the hepatic decompensation/ hepatic failure AE of special interest, the number and percentage of subjects experiencing at least one treatment-emergent AE in the search will

be presented by SOC and preferred term and across all SOCs/preferred terms. In addition, a by-subject listing of treatment-emergent AEs meeting the search criterion will be provided.

For the hepatocellular carcinoma AE of special interest, a by-subject listing of all post-baseline (i.e., including both treatment-emergent and non-treatment emergent) AEs meeting the search criterion will be provided.

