## **4.4 Planned Analyses**

All analyses will be conducted by statisticians and programmers at AbbVie or designees according to the methodologies specified in this SAP.

The primary analysis will occur after all subjects have completed the Post-Treatment Week 12 Visit or prematurely discontinued from the study. For the primary analysis, data will be locked after performing appropriate data cleaning.

The end-of-study analysis will be conducted when all subjects enrolled in the study have completed the Post-Treatment Week 24 Visit or prematurely discontinued from the study. Data collected after the primary analysis will be added to a new version of the database which will be cleaned and locked at the end of the study. Results from the final analysis will be described in the clinical study report (CSR).

There is no intention of stopping the study early based on efficacy findings the primary analysis. The intention is to follow all subjects who receive study drug for 24 weeks following treatment.

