#### **11.2.1 Treatment-Emergent Adverse Events**

Treatment-emergent AEs are defined as any AE with an onset date that is after the first dose of study drug and no more than 30 days after the last dose of study drug. Events where the onset date is the same as the study drug start date are assumed to be treatment-emergent. If an incomplete onset date was collected for an AE, the event will be assumed to be treatment-emergent, unless there is other evidence that confirms that the event was not treatment-emergent (e.g., the event end date was prior to the study drug start date).

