#### **11.2.4 Listings of Adverse Events**

The following listings of AEs will be prepared:

- All serious AEs (from the time the subject signed the study-specific informed consent through the end of the study),
- Treatment-emergent serious AEs,
- Treatment-emergent AEs leading to death,
- Treatment-emergent AEs leading to discontinuation of study drug,
- Treatment-emergent AEs leading to study drug interruption,
- AEs (treatment-emergent or all, as applicable) in each of the AEs of special interest categories.

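### The hepatic decompensation/failure listing stops 30 days after last dose, while the HCC listing covers all post-baseline time; extending it to match would cost little

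*SAP*

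**What the plan says.** Section 11.2.3 sets a separate rule for each of its two special-interest categories.

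- **Hepatic decompensation/failure**, identified by the sponsor's PMQ. The table gives "the number and percentage of subjects experiencing at least one treatment-emergent AE in the search will" be shown by SOC and preferred term. The listing has the same limit: "In addition, a by-subject listing of treatment-emergent AEs meeting the search criterion will be provided".
- **HCC**, identified by a set of preferred terms. There is no table, but "a by-subject listing of all post-baseline (i.e., including both treatment-emergent and non-treatment emergent) AEs meeting the search criterion will be provided".

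Section 11.2.1 defines treatment-emergent as onset after the first dose and "no more than 30 days after the last dose of study drug". Section 11.2.4 repeats the special-interest listings as "AEs (treatment-emergent or all, as applicable) in each of the AEs of special interest categories", which refers back to the rule for each category and does not widen either.

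On follow-up, section 4.4 says: "The intention is to follow all subjects who receive study drug for 24 weeks following treatment". Section 11.2.4 also plans a listing of "All serious AEs (from the time the subject signed the study-specific informed consent through the end of the study".

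**The concern.** The plan singles out two liver outcomes and reports them over different periods without saying why. The 30-day window is the plan's default for AEs, but the plan departs from it where later events matter. It does so for HCC, for serious AEs, and in section 11.3.2 for the listing of CKD worsening or dialysis start, which covers both the treatment and post-treatment periods. Decompensation/failure stays on the default.

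What is at stake is the content of a named safety output. If a subject's first decompensation event starts after Day 30, the special-interest table and listing will not show it. A reader who turns to those outputs for the liver safety picture would have to find the case by reading the general serious AE listing line by line.

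**Working it through.** The plan states no figure on this point, such as a late-event rate or an expected count, so there is none to reproduce. The check has three parts.

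**1. Share of planned follow-up outside the decompensation outputs**

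Inputs: treatment-emergent window of 30 days after last dose (section 11.2.1); follow-up of 24 weeks (section 4.4), nominal Day 168 (Table 3); treatment of 8, 12 or 16 weeks (section 4.2).

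- Post-treatment days: 24 × 7 = 168.
- Outside the window: 168 − 30 = 138, and 138/168 = 82%.
- Share covered from first dose to Post-Treatment Week 24 = (treatment days + 30)/(treatment days + 168):

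| Duration | Covered | Planned | Share |
|---|---|---|---|
| 8 weeks | 56 + 30 = 86 | 56 + 168 = 224 | 38% |
| 12 weeks | 84 + 30 = 114 | 84 + 168 = 252 | 45% |
| 16 weeks | 112 + 30 = 142 | 112 + 168 = 280 | 51% |

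The HCC listing has no such limit, so its uncovered share is 0%. These are fractions of calendar time, not of events.

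**2. What other planned outputs would show after Day 30**

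- *All serious AEs (section 11.2.4).* A late serious case is listed. The plan does not apply the PMQ there, and the case is not identified as special interest.
- *Child-Pugh shift tables (section 11.5; timing in the Table 3 note).* These reach Post-Treatment Weeks 12 and 24, in cirrhotic subjects only. The five components in Table 6 include ascites and encephalopathy but not variceal bleeding. An episode that resolves between visits may not register. A subject with no score at a visit is left out of the percentages.
- *Hepatic laboratory criteria (section 11.3.2).* These are summarized during treatment only.
- *Deaths (section 11.2.2, overview).* This row is separate from the one for treatment-emergent AEs leading to death, but it does not identify decompensation.

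The only case with no planned AE output is a non-serious decompensation event starting after Day 30. Whether such events are collected is a protocol matter and is not shown in the SAP.

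**3. How likely a late case is**

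The SAP gives no rate. As an assumption, take a probability p of 0.5% to 3% per cirrhotic subject, and n = 30, the approximate cap in section 4.2.

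- Expected late cases = n × p: 30 × 0.005 = 0.15, to 30 × 0.03 = 0.9.
- Chance of at least one = 1 − (1 − p)^30: 14% at p = 0.5%, 60% at p = 3%.

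One case would be 1/30 = 3.3% of cirrhotic subjects at the cap. The special-interest table is on the safety population across all arms (section 11.1), planned at about 120, where one case is 1/120 = 0.8%.

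**The case against.** The strongest reply is that nothing here is an error. The treatment-emergent window is the plan's general AE convention, the HCC listing is an explicit exception, and section 11.2.4 acknowledges that the windows differ by category. The rules are clear and can be programmed. This stands: the point concerns a reporting choice, not a contradiction.

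A reader might also infer that later decompensation is omitted from the report altogether. The documents do not support that. A subject admitted to hospital with decompensation on post-treatment Day 45 would have a serious AE and would appear in the serious AE listing, and Child-Pugh scores are tabulated to Week 24. If the protocol collects only serious AEs after Day 30, every late case that is collected is already listed somewhere. Nor does the SAP say that Child-Pugh is scheduled in order to detect decompensation; it gives only timing and tabulation. The PMQ terms are not shown either, so whether a given event would match is unknown.

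Finally, a count and percentage through the end of the study could mix all AEs up to Day 30 with serious AEs only thereafter, and would be hard to interpret. HCC itself gets no percentage. This also stands, and it is why the fix is confined to the listing.

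The reply does not explain why two special-interest liver outcomes are listed over different periods, and it does not make the serious AE listing a substitute for a special-interest one.

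**Conclusion.** The point holds as a cheap improvement, not as an internal error. The decompensation/failure table and listing leave 82% of the planned post-treatment days outside their scope. The HCC listing leaves none, and the plan gives no reason for the difference. No efficacy estimate or confidence interval is affected. The practical effect is that a late case, if one occurs, would not be identified in the output designed to identify it.

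It would be going too far to say that such cases disappear or that the planned table would be false. The table is defined as treatment-emergent, and late serious cases are listed elsewhere.

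The 82% rests on the nominal 168-day follow-up. The 14% to 60% chance of at least one late case rests on an assumed rate of 0.5% to 3% and on 30 cirrhotic subjects, and should be read only as showing that a late case is plausible.

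**What to change.** In section 11.2.3:

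1. Keep the treatment-emergent number and percentage as the tabulated summary for hepatic decompensation/failure.
2. Change the by-subject listing to all post-baseline AEs that match the PMQ, following the HCC rule of "including both treatment-emergent and non-treatment emergent" events. Flag each event as treatment-emergent or not, and show its onset day relative to last dose.
3. Add a footnote saying that later events have weaker attribution to study drug and that, depending on the protocol's collection rules, they may be limited to serious events.

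The wording in section 11.2.4 already accommodates this. If the sponsor prefers the present limit, one sentence giving the reason would close the point. The cost is a change of SAP text and a rerun of the same query without the 30-day limit on data already collected, with no effect on study conduct or on the efficacy analyses.

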#### **11.2.4 Listings of Adverse Events**

The following listings of AEs will be prepared:

- All serious AEs (from the time the subject signed the study-specific informed consent through the end of the study),
- Treatment-emergent serious AEs,
- Treatment-emergent AEs leading to death,
- Treatment-emergent AEs leading to discontinuation of study drug,
- Treatment-emergent AEs leading to study drug interruption,
- AEs (treatment-emergent or all, as applicable) in each of the AEs of special interest categories.

### **11.3 Analysis of Laboratory Data**

Data collected from the central and local laboratories, including additional laboratory testing due to a serious AE, will be used in all analyses.

#### **11.3.1 Variables and Criteria Defining Abnormality**

Hematology variables to be summarized include: hematocrit, hemoglobin, red blood cell (RBC) count, white blood cell (WBC) count, neutrophils, bands, lymphocytes, monocytes, basophils, eosinophils, platelet count, reticulocyte count, prothrombin time (PT), international normalized ratio (INR), and activated partial thromboplastin time (aPTT).

Chemistry variables to be summarized include: blood urea nitrogen (BUN), creatinine, total bilirubin, direct and indirect bilirubin, alanine aminotransferase (ALT), aspartate aminotransferase (AST), alkaline phosphatase, sodium, potassium, calcium, inorganic phosphorus, total protein, glucose, albumin, chloride, bicarbonate, magnesium, gamma-glutamyl transferase (GGT), creatinine clearance (calculated using Cockcroft-Gault), and eGFR by MDRD.

The definitions of toxicity grades for laboratory parameters are presented in [Table 10](#).

**Table 10. Definitions of Toxicity Grades 1, 2, 3, and 4 for Laboratory Values**

Test	Grade 1	Grade 2	Grade 3	Grade 4
ALT	> ULN – 3 × ULN	> 3 – 5 × ULN	> 5 – 20 × ULN	> 20 × ULN
AST	> ULN – 3 × ULN	> 3 – 5 × ULN	> 5 – 20 × ULN	> 20 × ULN
Alkaline Phosphatase	> ULN – 2.5 × ULN	> 2.5 – 5 × ULN	> 5 – 20 × ULN	> 20 × ULN
Total Bilirubin	> ULN – 1.5 × ULN	> 1.5 – 3 × ULN	> 3 – 10 × ULN	> 10 × ULN
Hemoglobin	< LLN – 100 g/L	< 100 – 80 g/L	< 80 g/L	--
Absolute Neutrophil Count	< LLN – 1.5 × 10  /L	< 1.5 – 1.0 × 10  /L	< 1.0 – 0.5 × 10  /L	< 0.5 × 10  /L
Platelet count	< LLN – 75.0 × 10  /L	< 75.0 – 50.0 × 10  /L	< 50.0 – 25.0 × 10  /L	< 25.0 × 10  /L
INR	> 1 – 1.5 × ULN	> 1.5 – 2.5 × ULN	> 2.5 × ULN	--
Creatinine clearance	< LLN – 60 mL/min	< 60 – 30 mL/min	< 30 – 15 mL/min	< 15 mL/min
Albumin	< LLN – 30 g/L	< 30 – 20 g/L	< 20 g/L	--
White blood cells	< LLN – 3.0 × 10  /L	< 3.0 – 2.0 × 10  /L	< 2.0 – 1.0 × 10  /L	< 1.0 × 10  /L
Lymphocyte	< LLN – 0.8 × 10  /L	< 0.8 – 0.5 × 10  /L	< 0.5 – 0.2 × 10  /L	< 0.2 × 10  /L
GGT	> ULN – 2.5 × ULN	> 2.5 – 5 × ULN	> 5 – 20 × ULN	> 20 × ULN
Glucose (high)	> ULN – 8.9 mmol/L	> 8.9 – 13.9 mmol/L	> 13.9 – 27.8 mmol/L	> 27.8 mmol/L
Glucose (low)	< LLN – 3.0 mmol/L	< 3.0 – 2.2 mmol/L	< 2.2 – 1.7 mmol/L	< 1.7 mmol/L
Creatinine	> ULN – 1.5 × ULN	> 1.5 – 3 × ULN	> 3 – 6 × ULN	> 6 × ULN
aPTT	> ULN – 1.5 × ULN	> 1.5 – 2.5 × ULN	> 2.5 × ULN	--
Sodium (low)	< LLN – 130 mmol/L	--	< 130 – 120 mmol/L	< 120 mmol/L
Sodium (high)	> ULN – 150 mmol/L	> 150 – 155 mmol/L	> 155 – 160 mmol/L	> 160 mmol/L
Potassium (low)	< LLN – 130 mmol/L	--	< 130 – 120 mmol/L	< 120 mmol/L
Potassium (high)	> ULN – 5.5 mmol/L	> 5.5 – 6.0 mmol/L	> 6.0 – 7.0 mmol/L	> 7.0 mmol/L
Magnesium (low)	< LLN – 0.5 mmol/L	< 0.5 – 0.4 mmol/L	< 0.4 – 0.3 mmol/L	< 0.3 mmol/L
Magnesium (high)	> ULN – 1.23 mmol/L	--	> 1.23 – 3.30 mmol/L	> 3.30 mmol/L

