### 11.3.2 Statistical Methods

The baseline value for clinical laboratory tests will be the last non-missing measurement on or before the day of the first dose of study drug. Values on Day 1 must also be before

the time of first dose if time is available. The same baseline value will be used for changes at Treatment Period visits and changes at Post-Treatment Period visits.

Changes from baseline to each post-baseline visit, including applicable post-treatment visits, will be summarized. Each protocol-specified laboratory parameter will be summarized with the sample size, baseline mean; visit mean; and change from baseline mean, standard deviation, minimum, median, and maximum.

Individual changes in the laboratory parameters listed in Section 11.3.1 will be tabulated using shift tables. Laboratory data values will be categorized as low, normal, or high based on normal ranges of the laboratory used for each sample. Shift tables from baselineto minimum value and maximum value during the Treatment Period will be created. For each parameter, the shift tables will cross tabulate the frequency of subjects with baseline values below/within the normal range to maximum above the normal range and with baseline values within/above the normal range to minimum below the normal range.

The laboratory parameters listed in Table 10 will be assigned a toxicity grade of 1, 2, 3, or 4. The number and percentage of subjects with a maximum toxicity grade of 1, 2, 3 or 4 will be tabulated. To be counted, the post-baseline value must have a toxicity grade that is more extreme than the toxicity grade corresponding to the baseline value. For each laboratory parameter in Table 10, the summary will also include the number and percentage of subjects with a maximum of at least grade 3. A listing of all relevant laboratory parameters will be provided for each subject who had an increase to grade 2 or higher for any laboratory variable in Table 10.

For CKD 3B and 4 subjects at screening, laboratory calculated eGFR by MDRD at Screening, EOT, and Post Treatment Week 4 will be summarized by mean, sd, minimum, maximum, median and interquartile range as well as by a box-plot.

CKD categorization at EOT is defined according to eGFR and requirement of dialysis in Table 4. For CKD 3B and 4 subjects at screening, number and percentage of subjects

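### Table 10 grades low potassium with the low-sodium limits, so the row gives no usable low-potassium toxicity grading

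*SAP*

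**What the plan says.** SAP Table 10 (Section 11.3.1) defines toxicity grades for laboratory values, with separate low and high rows for potassium.

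- The low row begins "Potassium (low) < LLN – 130 mmol/L", has no Grade 2, and gives Grades 3 and 4 as "< 130 – 120 mmol/L < 120 mmol/L".
- Two rows higher, the low row for sodium begins "Sodium (low) < LLN – 130 mmol/L" and continues with the same empty Grade 2 and the same Grade 3 and 4 limits.
- The high row for potassium begins "Potassium (high) > ULN – 5.5 mmol/L" and places Grade 4 above 7.0 mmol/L.

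Section 11.3.2 puts these grades to use in three outputs.

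- The table of maximum grade carries a worsening condition: "To be counted, the post-baseline value must have a toxicity grade that is more extreme than the toxicity grade corresponding to the baseline value".
- For every Table 10 parameter, "the summary will also include the number and percentage of subjects with a maximum of at least grade 3".
- A listing is produced for "each subject who had an increase to grade 2 or higher for any laboratory variable in Table 10".

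The shift tables in the same section do not use Table 10: "Laboratory data values will be categorized as low, normal, or high based on normal ranges of the laboratory used for each sample".

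**The concern.** The low-potassium limits are on the wrong scale. The table's own high-potassium row shows that potassium results here are single-digit numbers in mmol/L, so cut-offs of 120 and 130 cannot separate mild from severe low potassium. The row looks like a copy of the sodium row.

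Safety is part of the primary objectives (Section 4.1), the subjects have chronic kidney disease from Stage 3b to Stage 5, some on dialysis, and the sponsor chose to grade potassium in both directions. A low-potassium line that shows no events because of a table error could be taken as a safety finding. A line that shows every low value as Grade 4 would be a false signal. Someone who notices the slip while programming would have to pick limits that the SAP does not contain, and the grading would then no longer be pre-specified.

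**Working it through.** **Inputs.** The limits come from Table 10 and the worsening condition from Section 11.3.2. Two inputs are assumptions: a grid of potassium values from 1.0 to 10.0 mmol/L in steps of 0.1, chosen to reach beyond the table's highest potassium limit of 7.0, and an LLN of 3.3, 3.5 or 3.7 mmol/L, because the SAP gives no LLN.

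**Step 1: compare the rows (mmol/L).**

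| Row | Grade 1 | Grade 2 | Grade 3 | Grade 4 |
|---|---|---|---|---|
| Sodium (low) | below LLN, down to 130 | none | below 130, down to 120 | below 120 |
| Potassium (low) | below LLN, down to 130 | none | below 130, down to 120 | below 120 |
| Potassium (high) | above ULN, up to 5.5 | above 5.5, up to 6.0 | above 6.0, up to 7.0 | above 7.0 |

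The first two rows agree in 4 of 4 cells. The lowest cut-off in the low-potassium row (120) is about 17 times the highest cut-off in the high-potassium row (120 / 7.0 = 17.1).

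**Step 2: literal reading.** A value k is Grade 4 if k < 120. Every value from 1.0 to 10.0 meets this, so the only grade that occurs is 4. A subject is counted if the post-baseline grade exceeds the baseline grade, and 4 > 4 is false. Over all baseline and post-baseline pairs on the grid (91 × 91 = 8281), the number counted is 0.

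**Step 3: reading that also requires a value below the LLN.** Grade 1 would need a value below the LLN yet at least 130, and Grade 3 a value from 120 to below 130. No potassium value satisfies either, so a value is ungraded (at or above the LLN) or Grade 4 (below it). A pair is counted only when baseline is at or above the LLN and the later value is below it.

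| Assumed LLN | Grid values below | Grid values at or above | Pairs counted | Grade given |
|---|---|---|---|---|
| 3.3 | 23 | 68 | 23 × 68 = 1564 | 4 in all |
| 3.5 | 25 | 66 | 25 × 66 = 1650 | 4 in all |
| 3.7 | 27 | 64 | 27 × 64 = 1728 | 4 in all |

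These are numbers of grid combinations, not expected event rates. They show that every counted fall is Grade 4 whichever LLN is assumed, even a fall of 0.1 mmol/L across the limit. A subject already below the LLN at baseline could not be counted, however far the value fell.

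**Step 4: trace the outputs.**

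| Output in Section 11.3.2 | Uses the row? | Literal reading | With LLN requirement |
|---|---|---|---|
| Maximum-grade table, low potassium | yes | nobody with a baseline value counted | every fall from normal is Grade 4 |
| Grade 3 or higher summary, low potassium | yes | nobody with a baseline value counted | every fall from normal included |
| Grade 2 or higher listing, low-potassium trigger | yes | never triggers on an increase from a baseline grade | every fall from normal triggers |
| Same listing, triggers from other rows | no | unaffected | unaffected |
| Shift tables by normal range | no | unaffected | unaffected |
| Change from baseline | no | unaffected | unaffected |

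**The case against.** The best case on the other side accepts the copied row and disputes how far the damage reaches.

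- A reader might infer that low potassium disappears from the whole analysis. The SAP does not support that. The shift tables use each laboratory's normal range and cover falls below it, potassium is a listed chemistry variable, and change from baseline is summarised with its minimum. What is lost is the grading of severity.
- A reader might infer that the Grade 2 or higher listing cannot trigger at all. It triggers on any Table 10 parameter, so only the low-potassium trigger is affected.
- A reader might conclude that the low-potassium count must be zero for all of the roughly 120 subjects. That needs the Grade 4 cell to be read literally and a baseline potassium value for each subject. With an LLN requirement the error runs the other way. Nor does the document support saying that a subject without a baseline value would automatically be Grade 4: Section 11.3.2 gives no grading rule for that case.
- The row sits in a descriptive safety table. It does not touch SVR12, the secondary endpoints, the populations or the confidence intervals. No hypothesis is tested on the efficacy endpoints, and the adverse events of special interest are hepatic. Either output would look odd enough to be noticed in programming checks.

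The first three points stand and set the limits of the finding. The fourth limits its importance but does not remove it: noticing the error supplies no replacement limits, and nothing else in the SAP corrects the row.

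**Conclusion.** The point holds in a bounded form. The Potassium (low) row of Table 10 is the Sodium (low) row repeated in all four cells, and it contradicts the scale of the Potassium (high) row below it. The row is complete and well formed, so it does not look like a fault of text extraction.

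Three low-potassium outputs are unusable: the maximum-grade table, the Grade 3 or higher summary and the low-potassium trigger of the Grade 2 or higher listing. The direction of the error depends on programming. Under the literal limits 0 of 8281 grid pairs are counted. With an LLN requirement every fall below the LLN from a normal baseline is Grade 4, for each assumed LLN from 3.3 to 3.7 mmol/L. The conclusion rests on potassium values lying far below 120 mmol/L, which the table's own high row shows. It does not depend on the exact grid or LLN.

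It is a necessary correction with limited reach, and it should be made before the laboratory tables are programmed.

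**What to change.** Reconcile the Potassium (low) row of Table 10 with the sponsor's intended grading source, so that all its limits are on the potassium scale. The SAP names no toxicity scale in Section 11.3 or Table 10, so the replacement limits have to come from the sponsor, and none are proposed here. Then derive the three low-potassium outputs of Section 11.3.2 from the corrected row.

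The cost is one table row in the SAP and the matching entry in the programming specification. No design, sample size or efficacy analysis changes.
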